5.10.2 Laboratory data

For laboratory test covered by the Common Terminology Criteria for Adverse Events (CTCAE) version 3.0, the study's biometrics and statistical reporting team will grade laboratory data accordingly. Grade 5 will not be used.

In cases differentials count, the lower limits of normal ranges used in CTCAE definition have to be replaced by a clinical meaningful limit expressed in absolute counts.

For laboratory tests where grades are not defined by CTCAE, results will be graded by the low/normal/high classifications based on laboratory normal ranges.

Patients with laboratory abnormalities of CTC grade 3 or 4 will be listed. All laboratory data with values flagged to show the corresponding CTCAE grades and the classifications relative to the laboratory normal ranges will be listed.

For analyses performed by core baseline diabetic status, the core diabetic status is defined as follow:

- Diabetic: patients taking any antidiabetic medication, or with history of diabetic medication or HbA1c≥6.5% or FPG≥126 mg/dL
- Pre-diabetic: patients not qualifying as diabetic and with FPG \geq 100 mg/dL and < 126 mg/dL or HbA1c \geq 5.7% and <6.5%
- Normal glucose tolerance: patients not qualifying as diabetic or pre-diabetic and with FPG< 100 mg/dL and/ or HbA1c<5.7%.

Listing of all laboratory data with values flagged to show the corresponding CTCAE grades and the classifications relative to the laboratory normal ranges.

Laboratory summaries using all available data

The following summaries using all available data will be generated by phase (core/extension):

- For hematology, biochemistry and urinary laboratory tests where CTCAE grades are defined, shift tables using CTCAE grades to compare baseline to the worst post-baseline value
- For hematology, biochemistry and urinary laboratory tests where CTCAE grades are not defined, shift tables using the low/normal/high/high and low/missing classification to compare baseline to the worst post-baseline value
- For fasting serum cortisol and plasma ACTH, shift tables using the low/normal/high/high and low/missing classification to compare baseline to the worst post-baseline value will be generated.
- For fasting blood glucose and HbA1c, shift tables using the ADA (2010) to compare baseline to the last available value

- For fasting blood glucose and HbA1c, shift tables using the ADA (2010) to compare baseline to the last available value by baseline diabetic status
- For fasting blood glucose and HbA1c, summary of change from baseline over time
- For fasting blood glucose and HbA1c, summary of changes at the last value from baseline by baseline diabetic status

5.10.2.1 Liver function parameters

Liver function parameters of interest are total bilirubin (TBIL), ALT, AST and alkaline phosphates (ALP). The number (%) of subjects with worst post-baseline values will be summarized:

- ALT or AST > 3xULN
- ALT or AST > 5xULN
- ALT or AST > 8xULN
- ALT or AST > 10xULN
- ALT or AST > 20xULN
- TBL > 2xULN
- TBL > 3xULN
- ALT or AST > 3xULN & TBL >2xULN
- ALT or AST > 3xULN & TBL >2xULN & ALP < 2xULN

Potential Hy's Law events are defined as those subjects with concurrent occurrence of AST or ALT > 3xULN and TBL > 2xULN and ALP < 2xULN in the same assessment sample during the on-treatment period. Further medical review has to be conducted to assess potential confounding factor such as, liver metastases, liver function at baseline etc.

For more details and adaptation of above summary, please refer to the Oncology Hepatic Safety guidance.

5.10.3 ECG

A newly occurring ECG abnormality is defined as notable ECG abnormality at post-baseline but not at baseline. Clinically notable ECG abnormality is defined in Table 5-1. The percentage is calculated based on patients with both baseline and post-baseline evaluations. A patient with multiple occurrences of a newly occurring abnormality is counted only once for each abnormality.

The patients with newly occurring ECG abnormalities will be listed and the corresponding values will be flagged in the listing.

ECG summaries using all available data

The following summaries using all available data will be generated by phase (core/extension):

- For QTcF, QTcB and QT, shift tables to compare baseline to the worst post-baseline value
- The number of patients and percentage of patients with newly occurring ECG changes

Table 5-1 Clinicall	y notable ECG abnormalities
---------------------	-----------------------------

ECG value	Notable ECG abnormality
QT, QTcB, QTcF	New > 450
[ms]	New > 480
	New > 500
	Increase from baseline > 30
	Increase from baseline > 60
PR [ms]	Increase from baseline > 25% and > 200
QRS [ms]	Increase from baseline > 25% and > 110
HR [bpm]	Decrease from baseline > 25% and < 50
	Increase from baseline > 25% and > 100

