| 
A. pasireotide LAR injection and study visits every 28 days +/- 2 days.
 
B Patients' GH nadir within 2 hours after an oral glucose load with 75 g of glucose (OGTT) will be measured. The scheduled time points are at t0, oral glucose, t30, t60, t90, t120 (except for diabetic patients).
 
C Blood sampling of IGF-1 for PD assessment combines with efficacy assessment.
 
D For patients accepting to continue in the extension phase, at 12 months, a 13th injection of the same study treatment received in the core phase will be administered. Patients continuing the study treatment with pasireotide LAR in the extension phase will have the option of receiving pasireotide therapy as long as they do not fulfill any of the study discontinuation criteria or until pasireotide LAR is commercially available or until the pasireotide LAR development program is discontinued (whichever comes first).
 
Visit 21 and Visit 777 are on the same day for patients willing to continue in the extension phase.
 | | | | | | | | | | | | | | | | | | | | | |

[figure not shown]
[figure not shown]

Table 7-2 Extension Visit evaluation schedule

| | Category | Reference | | | | | | | | | | | | | | | | End of study treatment for Ext | Study completion |
|--|----------|------------|-----|-----|-----|-----|-----|-----|-----|-----|-----|-----|-----|-----|-----|-------------------------|-----|---------------------------------|------------------|
| Visit number | | | 21 | 22 | 23 | 24 | 25 | 26 | 27 | 28 | 29 | 30 | 31 | 32 | 33 | 34 and following visits | 778 | 779 | |
| Study day | | | 337 | 365 | 393 | 421 | 449 | 477 | 505 | 533 | 561 | 589 | 617 | 645 | 673 | 701, 729, 757, 813... | | 56 days following the last dose | |
| Month (1 month = 28 days) | | | 12 | 13 | 14 | 15 | 16 | 17 | 18 | 19 | 20 | 21 | 22 | 23 | 24 | 25- | | | |
| pasireotide LAR Injection ^A | D | 6.1 | 13 | 14 | 15 | 16 | 17 | 18 | 19 | 20 | 21 | 22 | 23 | 24 | 25 | 26- | | | |
| Physical Examination | S | 7.2.2.1 | | X | X | X | X | X | X | X | X | X | X | X | X | | X | X | |
| Vital signs | D | 7.2.2.2 | | X | X | X | X | X | X | X | X | X | X | X | X | | X | X | |
| Weight | D | 7.2.2.3 | | X | X | X | X | X | X | X | X | X | X | X | X | | X | X | |
| ECG | D | 7.2.2.5.1 | | | | X | | | X | | | X | | | X | | X | X | |
| Gallbladder ultrasound | D | 7.2.2.4.10 | | | | X | | | X | | | X | | | X | | X | | |
| Hematology | D | 7.2.2.4.1 | | | | X | | | X | | | X | | | X | | X | X | |

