4.1.2 Date of first administration of study drug

The date of first administration of study drug will be derived as the first date when a nonzero dose of study drug is administered and recorded on the dose administration record (DAR) page of the electronic case report form (eCRF). For the sake of simplicity, the date of first administration of study drug will also be referred as start date of study drug.

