4.1.5 Baseline

The baseline will be the last pre-treatment evaluation result within 28 days of the start date of study drug.

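### SAP 5.10.3 tabulates 'newly occurring' ECG abnormalities by phase but judges them only against the pre-treatment baseline, so the extension table mixes carried-over with late-onset abnormalities

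*SAP*

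**What the plan says.** SAP 5.10.3 defines the term: "A newly occurring ECG abnormality is defined as notable ECG abnormality at post-baseline but not at baseline". It adds a counting rule, "A patient with multiple occurrences of a newly occurring abnormality is counted only once for each abnormality", and a denominator, "The percentage is calculated based on patients with both baseline and post-baseline evaluations". The output is "The number of patients and percentage of patients with newly occurring ECG changes". It stands in a list introduced by "The following summaries using all available data will be generated by phase (core/extension", so core and extension each get their own summary.

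The reference point is set once for the whole SAP, in section 4.1.5: "The baseline will be the last pre-treatment evaluation result within 28 days of the start date of study drug". Section 4.1.2 ties that start date to the first non-zero dose in the study. No separate extension baseline is defined. Section 5.10.3 does not remove from the extension summary an abnormality already recorded in the core.

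The same section also plans by-phase shift tables for QT, QTcB and QTcF against baseline, and a listing of patients with newly occurring abnormalities in which the values are flagged.

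**The concern.** In a table split by phase, a reader will take the extension entry for *newly occurring* to mean abnormalities that arose during the extension. Under the SAP's definition it means abnormalities present during the extension that were absent before treatment. These differ whenever something that began in the core persists or returns.

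Late onset is a reasonable thing to look for with this drug. Protocol 1.2.1.2 describes two thorough QT studies that showed prolongation, Protocol 8.1.3 names QT prolongation as an adverse event of special interest, and Protocol 6.3.1 allows up-titration after Month 12. A table that blends carried-over with late-onset abnormalities could be misread as a signal emerging with long-term treatment.

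The denominator raises a second, smaller problem. It asks for a baseline and a post-baseline evaluation without saying in which phase.

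**Working it through.** The documents give no ECG count or rate that depends on this rule, so there is no plan figure to reproduce. The check applies the rule as written.

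**1. The rule in symbols.** For one patient and one abnormality, let B = notable at baseline, C = notable on at least one core ECG, E = notable on at least one extension ECG.

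- Core count: not B, and C.
- Extension count: not B, and E.
- The extension count splits into two parts: (not B, C, E) + (not B, not C, E).

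The first part is carried over or recurrent; only the second began in the extension. The surplus is the number of patients with not B, C and E. It is zero only if no core-onset abnormality is seen again on an extension ECG.

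**2. Does any other section remove the first part?** It would need an extension reference or an exclusion. SAP 4.1.2 closes the first route: "For the sake of simplicity, the date of first administration of study drug will also be referred as start date of study drug". SAP 5.10.3 contains no exclusion. A value at extension entry does exist: Protocol Table 7-1 schedules an ECG at Visit 777 (Day 337), and its footnote says "Visit 21 and Visit 777 are on the same day for patients willing to continue in the extension phase". The SAP does not use that value as a reference.

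**3. Illustration.** These are five invented QTcF patterns (ms), one patient each, judged by the New > 450 criterion of SAP Table 5-1. They are not trial data.

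| Pattern | Baseline | Core ECGs | Extension ECGs | Core count | Extension: SAP rule | Extension: against last core ECG (Day 337) | Extension: first onset only |
|---|---|---|---|---|---|---|---|
| A: begins in core, persists | 430 | 440, 460, 462 | 461, 463 | yes | yes | no | no |
| B: begins in core, resolves | 430 | 440, 460, 440 | 440, 441 | yes | no | no | no |
| C: begins in extension | 430 | 440, 441, 442 | 461, 463 | no | yes | yes | yes |
| D: begins in core, resolves, recurs | 430 | 460, 440, 440 | 460, 440 | yes | yes | yes | no |
| E: present at baseline | 455 | 456, 458, 460 | 461, 460 | no | no | no | no |
| **Total** | | | | **3** | **3** | **2** | **1** |

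Of the three extension counts under the SAP rule (A, C, D), only C began in the extension. Pattern B shows the limit of the point: an abnormality that resolves in the core and does not return is not counted again. Pattern D shows that a Day 337 reference alone would still count a recurrence as new.

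**4. Denominator.** Let N be the patients with a baseline and any post-baseline ECG, and M the patients with a baseline and at least one extension ECG, so M ≤ N. Read literally, the extension percentage is n/N, because a patient with core ECGs who never entered the extension still qualifies. Restricted to the phase it is n/M. The literal version is smaller by the factor M/N. The documents do not give M. SAP 4.1.10 does set phase-specific denominators for response rates; section 5.10.3 has no counterpart.

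**5. Denominator for first onset.** A patient already affected at baseline or in the core cannot have a first onset in the extension. In the illustration, A, B and D leave because of the core and E because of baseline, so the first-onset row is 1/1. Dividing by all five with an extension ECG would give 1/5 and understate the rate among those at risk.

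**The case against.** The strongest reply is that the column reports what the SAP says it reports. *Newly occurring* is defined as absent at baseline. The pre-treatment reference is used throughout the by-phase laboratory, ECG and vital-sign shift tables, and most Table 5-1 criteria are themselves changes from baseline. Comparison with pre-treatment is a legitimate description of what is present during the extension. This stands, and it is why the comparison should be kept; what remains is the label and the missing first-onset count.

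Three stronger readings are tempting, and the documents do not support them.

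- A reader might infer that the double count breaks the count-once rule. That sentence names no phase. Applied within each summary, which is its natural reading, nothing is broken. Applied across phases, the patient is counted once and only the choice of phase is open. The scope is unstated, which is an ambiguity and not a contradiction.
- A reader might infer that the table defeats the objective on safety in the extension phase. In both documents' Table 3-1, that objective is assessed by graded adverse events. ECGs are named under total-group long-term safety, for which a pre-treatment reference is natural.
- A reader might infer that persistence cannot be told from late onset. This is true of the table only. SAP 5.10.3 flags the values in a patient listing, SAP 4.1.4 puts study day in the listings, and only 33 patients were randomized. The extension schedules ECGs at Visits 24, 27, 30 and 33 plus Visits 778 and 779, so the sorting can be done by hand.

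On the denominator, SAP 5.1 refers generally to the relevant population or subgroup, which a programmer might take as phase-restricted. It does not say so.

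**Conclusion.** The point holds as a matter of labelling and scope. As written, an abnormality that starts in the core and appears on any extension ECG is counted as newly occurring in both phases, and the extension percentage has no stated phase-specific denominator. This rests on the plain text of SAP 4.1.2, 4.1.5 and 5.10.3, and on at least one core-onset abnormality persisting or recurring on an extension ECG.

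The size cannot be computed from the documents. A reader might try to estimate it. For example, 25 entrants, 20–40% with core onset and 50–80% of those recurring would give 25 × 0.20 × 0.50 = 2.5 to 25 × 0.40 × 0.80 = 8 patients, or 10–32%. Every one of those inputs is an assumption with no anchor in the protocol or SAP, so the range is not evidence about this trial.

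The table is descriptive. The primary endpoint, its confidence interval and all error rates are untouched, so this is a minor improvement.

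**What to change.** In SAP 5.10.3:

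1. Keep the comparison with the pre-treatment baseline, but label the extension row *present in extension, not at baseline*. Use as denominator the patients with a baseline and at least one extension ECG.
2. Add a first-onset row for the extension, counting abnormalities absent at baseline and at every core ECG. Use as denominator the patients with an extension ECG who were free of that abnormality at baseline and throughout the core; this denominator will differ between abnormalities.
3. State that the count-once rule applies within each phase summary.

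The cost is one derivation flag and one extra row. No new data are needed, because the core ECGs, including Day 337, are already scheduled. The first-onset denominators may be small, so show them beside the percentages.

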13. Patients with risk factors for torsade de pointes, i.e. patients with a baseline QTcF > 470 ms, hypokalemia, hypomagnesemia, hypocalcemia, family history of long QT syndrome, or patients receiving a concomitant medication known to prolong QT interval.
14. Patients with confirmed central hypothyroidism, central hypoadrenalism and diabetes insipidus, unless they are adequately treated with stable doses of hormone replacement therapy for a minimum of three months prior to study entry (first dose of study medication). Patients with confirmed central hypogonadism unless they are adequately treated with stable doses of hormone replacement therapy for a minimum of three months prior to study entry (first dose of study medication) except in cases where hormones replacement therapy is not indicated.
15. Patients with history of liver disease such as cirrhosis, chronic active hepatitis B or C, or patients with ALT or AST more than 2 x ULN, baseline total bilirubin > 1.5 x ULN
16. Presence of Hepatitis B surface antigen (HbsAg)
17. Presence of Hepatitis C antibody (anti-HCV)
18. Patients with WBC <3 x 10⁹/L; Hgb < 90 % LLN; PLT <100 x 10⁹/L
19. Patients who have any current or prior medical condition that may interfere with the conduct of the study or the evaluation of its results in the opinion of the Investigator
20. Female patients who are pregnant or lactating, or are of childbearing potential (defined as all women physiologically capable of becoming pregnant) and not practicing an effective method of contraception/birth control. Female patients of child bearing potential and sexually active males must use a condom during intercourse while taking the drug and for 3 months after the last dose of study drug and should not father a child in this period. A condom is required to be used also by vasectomized men in order to prevent delivery of the drug via seminal fluid. Effective contraception methods include:
 - Use of oral, injected or implanted hormonal methods of contraception
 - Placement of an intrauterine device or intrauterine system
 - Barrier methods of contraception: condom or occlusive cap (diaphragm or cervical/vault caps) with spermicidal foam/gel/film/cream/ vaginal suppository
 - Total abstinence
 - Patient sterilization (male or female)
21. Patients who have a history of alcohol or drug abuse in the 12 month period prior to receiving pasireotide LAR

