		3. Safety disclosure section with two tables related to adverse events (non-serious AE and death due to SAE) are added in order to comply with legal requirements pertinent to the disclosure of study results (Section 5.10.1)

1 Introduction

This document describes the detailed statistical methodology of the Report Analysis Plan (RAP) of Study SOM230C1202 required for reporting the results of final clinical study report (CSR).

The first analysis, for the purpose of the First Interpretable Results (FIR) only, was conducted when the last patient completed the Month 3 assessment with data cut-off date on 31-Jul-2014. The second analysis was conducted, when the last patient completed the Month 12 assessments (with data cut-off date on 2-Apr-2015), and the results were reported in an interim CSR dated 01-Jul-2015. Details on the final analysis are provided in the Section 4.2 for final CSR. For completeness a short description of prior analysis is provided in the same section.

[figure not shown]
Data will be analyzed by Novartis personnel or a designated third party. This RAP contains relevant statistical considerations for the final analysis which will contain cumulative data generated from first patient first visit (FPFV) to last patient last visit (LPLV) until all patients have withdrawn study. Further supportive statistical information will be provided in the [Appendix 16.1.9 of the CSR].

2 Study design

A total of 33 eligible patients were enrolled and randomized to one of 3 doses of pasireotide LAR (20 mg, 40 mg, or 60 mg) in a ratio of 1:1:1. Randomization was stratified by prior medications (e.g. somatostatin analogues or dopamine agonists), (yes or no). Intramuscular administration of pasireotide LAR has been repeated every month (1 month = 28 days) for 12 months in core phase. It is permitted to increase the dose up to 60 mg in a patient showing the following biochemical test results after 3 and 6 months of study treatment: mean GH levels $\geq 2.5 \,\mu\text{g/L}$ and/or IGF-1 > ULN (age and sex related). In the event of any problem with tolerability, it is permitted to reduce the next lower dosage level at any time. After 3 months of study treatment, the primary endpoint (proportion of patients with a reduction of mean GH levels to $\leq 2.5 \,\mu\text{g/L}$ and normalization of IGF-1 to within normal limits) will be evaluated.

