5.1 General presentation of descriptive summaries

Categorical data (e.g. gender, race, etc.) will be summarized by frequency count and percentages. Percentages will be calculated using the number of patients in the relevant population or subgroup as the denominator.

Continuous data (e.g. age, body weight, etc.) will be summarized by appropriate descriptive statistics (i.e. mean, standard deviation, median, minimum and maximum).

Data through 24 months of study treatment and at end of study treatment will be summarized except for study disposition, drug administration record and adverse events/serious adverse events. For study disposition, drug administration record and adverse events/serious adverse events, all data even beyond 24 months of study treatment will be summarized and listed.

All data will be listed appropriately.

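### The denominator for newly occurring ECG abnormalities in SAP 5.10.3 includes patients who cannot be events in some absolute-threshold QT rows, so those rows can understate the rate among patients at risk

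*SAP*

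**What the plan says.** SAP 5.10.3 defines the event: "A newly occurring ECG abnormality is defined as notable ECG abnormality at post-baseline but not at baseline". It defines the denominator in the same paragraph: "The percentage is calculated based on patients with both baseline and post-baseline evaluations". A patient is counted at most once per abnormality, so each line of SAP Table 5-1 is its own category.

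Table 5-1 has two kinds of line:
- **Absolute limits** for QT, QTcB and QTcF: new values above 450, 480 and 500 ms.
- **Change-based criteria**: QT/QTc lines such as "Increase from baseline > 30" (and the same at 60 ms), and PR, QRS and heart-rate lines of the form "Increase from baseline > 25% and > 200".

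The general rule in SAP 5.1 is: "Percentages will be calculated using the number of patients in the relevant population or subgroup as the denominator". SAP 4.1.5 fixes the reference value: "The baseline will be the last pre-treatment evaluation result within 28 days of the start date of study drug". Protocol 5.3, criterion 13, excludes "patients with a baseline QTcF > 470 ms" and sets no limit on QTcB or uncorrected QT.

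The number and percentage of patients with new ECG changes are to be tabulated by phase (core, extension). The same section plans shift tables for QTcF, QTcB and QT and a listing of patients with new abnormalities.

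**The concern.** The numerator and the denominator describe different groups. For an absolute limit, someone above it before the first dose is barred from being an event, yet still adds one to the denominator. The percentage is then lower than the proportion of patients who crossed the limit among those who could cross it. The error can only go in that direction.

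QT prolongation is a recognised risk here. Protocol 1.2.1.2 describes two thorough QT studies showing an effect, Protocol 6.3.3.2 gives QT its own management rules, and Protocol 8.1.3 names it as an event of special interest. A table headed as newly occurring changes will naturally be read as the risk of a new abnormality in patients who did not already have it.

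**Working it through.** **Inputs**
- x: patients with a new abnormality in a row. Not given in the documents; x = 3 is used for illustration.
- N: patients with a baseline and a post-baseline ECG. SAP section 2 states: "A total of 33 eligible patients were enrolled and randomized". N = 33 assumes that all of them are evaluable. N will be smaller in the extension if not all continue.
- b: patients above that row's limit at baseline. Not given in the documents; varied from 0 to 10.

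Neither document states an ECG rate, so there is no planned figure to reproduce.

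**Step 1: rows in which b can exceed zero**

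| Row | Can an eligible patient already be above the limit? |
|---|---|
| QTcF 'New > 450' | Yes: baseline above 450 and up to 470 ms passes criterion 13 |
| QTcF 'New > 480', 'New > 500' | No: baseline above 470 ms is excluded, so b = 0 |
| QT and QTcB 'New > 450', 'New > 480', 'New > 500' | Yes: no entry limit |
| QT/QTc increase > 30 or > 60 ms | No: the change at baseline is zero by definition, so b = 0 |
| PR, QRS, heart rate | No: each needs a change of more than 25% from baseline, so b = 0 |

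**Step 2: size**

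Reported percentage = x/N. Percentage among patients at risk = x/(N - b). Reported divided by at-risk = (N - b)/N; the inverse, N/(N - b), is how much higher the at-risk figure is.

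With N = 33:

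| b | N/(N - b) | x = 3: reported | x = 3: at risk |
|---|---|---|---|
| 0 | 33/33 = 1.000 | 9.1% | 3/33 = 9.1% |
| 1 | 33/32 = 1.031 | 9.1% | 3/32 = 9.4% |
| 2 | 33/31 = 1.065 | 9.1% | 3/31 = 9.7% |
| 3 | 33/30 = 1.100 | 9.1% | 3/30 = 10.0% |
| 5 | 33/28 = 1.179 | 9.1% | 3/28 = 10.7% |
| 10 | 33/23 = 1.435 | 9.1% | 3/23 = 13.0% |

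The relative factor does not depend on x. One to three patients above the limit at baseline make the at-risk rate a relative 3% to 10% higher. In the example that is 0.3 to 0.9 percentage points, less than the 1/33 = 3.0 points that a single patient contributes.

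**Step 3: whether another passage narrows the denominator**

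SAP 5.1 refers to the relevant population or subgroup without tying it to baseline status, and 5.10.3 then names its own denominator. Neither removes patients already above a limit.

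**The case against.** The strongest reply is that the denominator is declared and coherent: the share of evaluable patients who developed the abnormality. The SAP never calls it an at-risk rate, and it reports the count as well. The effect is conditional on baseline values that the documents do not show, it is probably small, and nothing inferential rests on it. All of this stands as an argument for a low priority. It does not answer the point that a percentage labelled as newly occurring includes patients who cannot be events.

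A second reply is that QT findings appear elsewhere: in the baseline-to-worst shift tables, in the listing of patients with new abnormalities, and in the special-interest adverse event tables of SAP 5.10.1. This is correct, so a reader should not infer that the table is the only source on new QT abnormality. The shift tables would give the at-risk denominators if they used the 450, 480 and 500 ms cut-offs, but SAP 5.10.3 does not state their categories.

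Three stronger inferences are also tempting and are not supported:
- **That all the new-QT percentages are too low.** Step 1 shows that they are not. QTcF is the measure behind the protocol's QT action rules (above 470 and above 500 ms), and its 480 and 500 ms rows are untouched among eligible patients.
- **That patients above a limit at baseline will be present.** Criterion 13 permits a QTcF above 450 and up to 470 ms; it does not show that anyone had one.
- **That the understatement differs between core and extension.** It could, if the share with a long baseline QT differs among those who continue, but the documents give no data on this.

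**Conclusion.** The point holds for seven rows: QTcF 'New > 450', and 'New > 450', 'New > 480' and 'New > 500' for each of QT and QTcB. In these rows the planned percentage understates the rate among patients at risk by the factor (N - b)/N whenever b is above zero. With N = 33 and b = 1 to 3, the at-risk rate is a relative 3% to 10% higher than the reported one; with b = 0 the two agree. A large effect, such as the relative 44% at b = 10, needs nearly a third of the cohort above the limit at baseline, and nothing in the documents indicates that.

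This rests on all 33 randomized patients being evaluable and on b being treated as unknown. For the two unaffected QTcF rows it also rests on criterion 13 having been applied to the reading used as the analysis baseline, with no ineligible patient enrolled. The matter is minor and descriptive; no test, sample size or primary result depends on it.

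**What to change.** In SAP 5.10.3, state that for each 'New > 450', 'New > 480' and 'New > 500' row of QT, QTcB and QTcF the denominator is the patients with a post-baseline ECG in that phase whose baseline value is at or below that row's limit. Print n/N in every row. Keep the present denominator for the change-from-baseline rows (QT/QTc increases, PR, QRS, heart rate). Applying the rule to QTcF 480 and 500 ms as well is harmless, because the denominator does not change when b = 0.

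The cost is one sentence and a per-row denominator in one table. No new data are needed.
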